11.4 Breaking the Blind

Breaking the blind in a clinical study on an emergency basis by the site should only occur when knowledge of the treatment to which a subject was allocated would have implications for the emergency medical management of the subject, if required for regulatory reporting, or if there is a pregnancy during the pregnancy reporting period.

If necessary, emergency breaking of the blind can be conducted through the IRT by the Investigator or other registered site users and/or the Medical Monitor. Whenever possible, the Investigator should contact the Medical Monitor before an emergency unblinding. Reason for

unblinding, person conducting the unblinding, personnel who know the unblinded treatment, and date/time of unblinding will be recorded.

12. Study Procedures and Guidelines

Table 1 provides the schedule of assessments depicting the required testing procedures to be performed for the duration of the study. When multiple evaluations are scheduled at the same time point, the priority for each will be as follows:

- At the clinic:
 - 1) UAS7, forms, and Atopic Conditions Questionnaire.
 - 2) Vital signs will be obtained after the subject has been at rest for ≥ 5 minutes.
 - 3) Physical examinations can be performed, and urine samples can be collected either before or after other evaluations, unless otherwise specified.

12.1 Pharmacodynamic/Efficacy-Related Procedures

12.1.1 Urticaria Patient Daily Diary

All subjects will be provided with an Urticaria Patient Daily Diary (UPDD) (Appendix 1). The subjects will receive clear instructions on the completion of the diary. UPDD includes UAS7 (itch and hives) for CSU subjects for clinical symptoms and activity interference. Subinvestigators and subjects will receive appropriate training and guidance on the use of the UPDD.

12.1.2 Weekly Urticaria Activity Score

The UAS7 is the sum for 7 days of the daily Hives Severity Score (HSS) and the daily Itch Severity Scale (ISS) score. The possible range of the weekly UAS7 score is 0–42. Complete UAS7 response is defined as UAS7 = 0 or by reduction of \geq 90% from baseline.

12.1.3 Hives Severity Score

The severity of hives will be recorded by all subjects once daily in their UPDD, on a scale of 0 (none) to 3 (>50 hives) (Table 3). A weekly HSS7 is derived by adding the average daily scores of the 7 days preceding the visit. Therefore, the possible range of the weekly score is 0-21. A complete hives response is defined as HSS7 = 0. When one or more of the daily scores are missing, the following principles will be applied to handle the missing data:

- At baseline and post-baseline time points, if a subject has at least 4 non-missing daily scores within a given week, the weekly score is calculated as the sum of the available scores in that week, divided by the number of days that have a non-missing diary score, multiplied by 7.
- At post-baseline time points, if there are less than 4 non-missing daily scores within a given week, then the weekly score is set to missing for the week. Missing data will be imputed using methods outlined in the SAP. It is worth remarking that missing data imputation is not required at baseline since a minimum of 4 daily scores per week are required to determine subject eligibility for the study.

Table 3 Hives Severity Score

[figure not shown]
Score	Number of Hives per 24 Hours
0	None
1	< 20
2	20-50
3	> 50

[figure not shown]
12.1.4 Itch Severity Score

The severity of itching will be recorded by all subjects once daily in their UPDD, on a scale of 0 (none) to 3 (severe) (Table 4). A weekly ISS7 is derived by adding the average daily scores of the 7 days preceding the visit. Therefore, the possible range of the weekly score is 0-21. A complete itch response is defined as ISS7 = 0. Partially missing diary entries will be handled in the same way described for the hives severity score.

 Table 4
 Itch Severity Score

Score	Pruritus (Itch) over the Last 24 Hours
0	None
1	Mild (present but not annoying or troublesome)
2	Moderate (troublesome but does not interfere with normal daily activity or sleep)
3	Severe (severe itching, which is sufficiently troublesome to interfere with normal daily activity or sleep)

12.1.8 Atopic Conditions Questionnaire

On Day 1 and Day 85, subjects will be prompted to answer additional questions about severity of symptoms related to asthma, allergic rhinitis, and allergic conjunctivitis (Appendix 5).

12.1.9 Photographs

The site staff may take photographs of subjects' CSU disease to track study drug response and disease progression. This will depend on the sites' standard operating procedures regarding photography. Subjects will be consented before the Sponsor will have access to any images.

12.1.10 Complete Blood Count with Differential

Blood for CBC with differential, including absolute blood eosinophil count, will be obtained at screening, just prior to each SC injection, and 1 hour (±15 minutes) after the end of each SC injection, as well as on all follow-up days 85, 127, and 155 (±5) or 14, 56, and 84 (±5) days after last dose, if ET. The blood sample will be processed and shipped in accordance with the Laboratory Manual and lab kit instructions. A central laboratory will analyze the blood sample and provide results for CBC with differential including hemoglobin, hematocrit, platelet count,

red blood cell count, white blood cell count, and absolute differential count (neutrophils, lymphocytes, monocytes, eosinophils, and basophils).

During the double-blind period, all differential blood counts from Day 1 (post-dose) through the end of the subject's participation will be blinded to the Sponsor and the site. An unscheduled CBC may be collected at the request of the Safety Monitor. The blood differential test results (neutrophils, eosinophils, basophils, monocytes, and lymphocytes) will be blinded from the Investigator and Sponsor from post-dose Day 1 through Day 155 or ET and until database lock has occurred. If a subject continues to the OLE period of the study, all differential blood counts will be blinded for the first (OLE Day 1) predose assessments and will be unblinded after the subject has received the first dose of the study drug.

As described in the Investigator's Brochure, changes in certain lab results are a part of the expected effects of lirentelimab and could potentially introduce bias in blinded members of the study. The Safety Monitor will have real-time access to these laboratory results and will review and escalate any concerns/issues to the Medical Monitor and/or the site as appropriate. An unscheduled CBC with differential may be collected if requested by the Safety Monitor. All panic alerts for blinded values will be sent to the Safety Monitor and evaluated in real time.

12.1.11 Fresh biopsies

At selected US sites only: Optional lesional (if available) and nonlesional skin biopsy samples will be collected at selected sites for exploratory analysis at baseline/predose on Day 1 and post-dose at either Day 57, Day 71, or Day 85 during the double-blind period. These fresh biopsies will be shipped overnight to the Sponsor for additional cell phenotyping and other exploratory analysis. Once the Sponsor receives the biopsies, they will be dissociated into single cells and immunophenotyped for immune cell populations (lymphocytes, eosinophils, basophils, mast cells, neutrophils, and macrophages) and other exploratory analysis. Detailed instructions on collection, packaging and shipping will be included in the lab manual. All materials required for shipment of the additional samples will be provided to the site by the Central Laboratory.

12.2 Safety-Related Procedures

12.2.1 Concomitant Medications

All concomitant medication and concurrent therapies will be documented at screening and at study visits if changes are made. Dose, route, unit, frequency of administration, indication for administration, and dates of medication will be captured. Any prior medication received within 30 days before screening and during the study through Day 155 or 84 (±5) days after last dose of

study drug, if ET, or through the first dose of study drug if the subject enters the OLE period of the study will be recorded.

For subjects participating in the OLE period, concomitant medications should be recorded in the AK002-027 double-blind treatment period database up until the first OLE dose is administered after the Day 85 (OLE Dose 1) visit. Rescue medications and procedures must be documented as rescue treatment in the source documents and on the Prior and Concomitant Medications eCRF.

Any medications taken for CSU or CSU-related symptoms at any time (even if longer than 30 days before screening) should be listed as concomitant medications, even if the medication was discontinued prior to study participation.

12.2.2 Complete Physical Examination

A complete physical exam will be performed by either the Investigator or a qualified designee during the screening visit. A complete physical exam will include the following body system or organ assessments: skin; head, eyes, ears, nose, and throat; thyroid; lungs; cardiovascular; abdomen; extremities; lymph nodes; and a brief neurological examination.

12.2.3 Body Weight and Height

At screening, height (in cm) and weight (in kg) will be measured by the site and recorded. The site cannot use values stated by the subject. Body weight will also be measured on all dosing and follow-up days or 14, 56, and 84 days after last dose if ET.

12.2.4 Symptom-Directed Physical Examination

A symptom-directed physical exam of reported or observed subject symptoms warranting examination in the opinion of the Investigator, including assessments of possible injection site reactions and IRR, will be performed by either the Investigator or a qualified designee at all study visits during the treatment period and follow-up period. New, abnormal physical exam findings must be documented and will be followed by the Investigator or Subinvestigator at the next scheduled visit or sooner if clinically indicated or referred to a non-study physician.

12.2.5 Electrocardiogram

An ECG will be obtained during screening after the subject has been in the resting position for ≥5 minutes and before any blood draw. The Investigator or Subinvestigator will review and assess any abnormalities on the ECG in terms of clinical significance. The ECG (without intensive QT analysis) will be used to identify diseases or conditions that would put the subject at increased risk if participating in a clinical study, so this should be taken into consideration when evaluating eligibility for entry into the study.

12.2.6 Previous CSU Diagnosis and Treatments Review

During the screening visit the Investigator or designee will collect documentation supporting the CSU diagnosis and ask the subject about the various treatments or methods of symptom control that they have tried in relation to their CSU symptoms. The treatments may include medications (prescription or over-the-counter) or adaptive behaviors as well as alternative medicine (i.e., acupuncture or hypnotic therapy). Any previous therapies and medications as related to subjects' CSU disease will be recorded in the study CRF.

Required specific source documentation supporting the assessment of inclusion and exclusion criteria regarding history of CSU diagnosis and treatments will be the following:

- For Inclusion Criteria #3, documentation of duration and a confirmed diagnosis of CSU should be supported by medical records and/or current documentation by the treating/study dermatologist (or allergist/immunologist) that the subject has a diagnosis of CSU which has been present for at least 6 months before screening based on patient interview.
- For Inclusion Criteria #4, the diagnosis of moderate-severe CSU refractory to H1-AH at a minimum of the licensed dose and at licensed frequency should be supported by treating/study dermatologist's (or allergist/immunologist) documented assessment at screening based on medical records or discussion with a referring physician.
- For Inclusion Criteria #6, the required stable dose of H1-AH between 1x and 4x of the licensed dose and at licensed frequency for treatment of CSU at least 1 week prior to screening needs to be confirmed by medical records and/or treating/study dermatologist's (or allergist/immunologist) notes.
- For Exclusion Criteria #3, the demonstrated lack of primary response to treatment with a biologic therapy (e.g. omalizumab) for the treatment of CSU should be confirmed by medical records and/or notes from the treating/study dermatologist (or allergist/immunologist).

More details are provided in the instructions on the eCRF pages and Study Reference Manual.

12.2.7 Vital Signs

Vital signs including systolic and diastolic blood pressure, pulse, body temperature, and respiratory rate will be taken after the subject has been at rest for ≥5 minutes and before any blood draw (except for post-SC injection when vital signs will be obtained as described below).

Vital signs will be measured at screening, on Day 8 (\pm 3), on all follow-up days or 14, 56, and 84 (\pm 5) days after last dose if ET, and on all dosing days within 30 (\pm 5) minutes predose, 15 (\pm 5) minutes after completion of the SC injection, and just prior to discharge.

Additional vital signs measurements may be collected at the Investigator's discretion if an IRR occurs. Vital signs including systolic and diastolic blood pressure, pulse, body temperature, and respiratory rate will be measured after the subject has been at rest for ≥5 minutes and before any blood draws have been obtained (unless collected for an IRR). Please refer to the schedule of assessments in Table 1.

12.3 Clinical Laboratory Measurements

Blood and urine samples for clinical safety laboratory tests will be collected at the time points described below. Investigators may have additional laboratory tests performed for the purpose of planning treatment administration or following AE or abnormal laboratory values.

The site will process and ship blood and urine samples per central laboratory instructions. A central laboratory or designee will analyze blood and urine samples and provide results for the following clinical safety laboratory tests.

Clinical laboratory testing may be performed locally, if necessary, with prior approval from Allakos. The site will strive to use the central laboratory whenever possible.

For any laboratory test value outside the reference range, the Investigator will determine clinical significance: Not Clinically Significant (NCS) or Clinically Significant (CS). An abnormal laboratory value should be deemed CS if any of the following conditions are met:

- The abnormality suggests a disease and/or organ toxicity that is new or has worsened from baseline.
- The abnormality is of a degree that requires additional active management, e.g., change of study drug dose, discontinuation of the study drug, close observation, more frequent follow-up assessments, or further diagnostic investigation.

Therefore, a clinically significant lab value is one that indicates a new disease process, an exacerbation or worsening of an existing condition, or requires further action to be taken. For any laboratory test value outside the reference range that the Investigator considers clinically significant, the Investigator will:

- Repeat the test to verify the out-of-range value.
- Follow the out-of-range value to a satisfactory clinical resolution.

- Record as an AE any laboratory test value after start of study drug that:
 - The Investigator considers clinically significant.
 - Requires a subject to be discontinued from the study.
 - Requires a subject to receive treatment.

Blood will be obtained for CBC with differential as described in Section 12.1.10.

12.3.1 Blood Chemistry Profile

Blood for chemistry, including hCG and FSH (only for screening), will be collected. Subjects of childbearing potential and postmenopausal women are required to undergo serum hCG or FSH testing (as described in Section 12.3.2). Blood for chemistry will be obtained during screening, predose on all dosing days, as well as on follow-up days 85, 127, and 155 or 14, 56, and 84 (\pm 5) days after last dose if ET.

The blood sample will be processed and shipped in accordance with the Laboratory Manual and laboratory kit instructions. A central laboratory will analyze the serum sample and provide results for chemistry tests including sodium, potassium, chloride, bicarbonate, glucose, blood urea nitrogen, creatinine, creatine kinase, calcium, phosphorus, magnesium, total and direct bilirubin, total protein, albumin, aspartate aminotransferase (AST), alanine aminotransferase (ALT), alkaline phosphatase, gamma-glutamyl transferase (GGT), and lactate dehydrogenase.

12.3.2 Pregnancy Test and Follicle-Stimulating Hormone

A serum pregnancy test (hCG level) will be completed for all female subjects of childbearing potential. Women who are surgically sterile (tubal ligation, partial or total hysterectomy, or bilateral oophorectomy) for at least 3 months or those who are postmenopausal for at least 1 year with FSH level >30 mIU/mL are not considered to be of childbearing potential. At screening, FSH levels will be tested on female subjects to confirm postmenopausal status. Both FSH and hCG samples will be processed by the central laboratory.

Subjects with FSH levels ≤30 mIU/mL will be considered to be of childbearing potential. Blood will be collected for serum pregnancy test at screening. Urine will be collected for dipstick pregnancy test on all dosing days, Day 8, and all follow-up days (or 14, 56, and 84 (±5) days after last dose of study drug if ET) for all subjects of childbearing potential. Test kits will be supplied by the central laboratory. Tests will be completed on site and evaluated prior to each SC injection. If a subject has a positive pregnancy test, dosing will immediately be discontinued.

To ensure subject safety, each pregnancy in a subject that received study drug must be reported within 24 hours of learning of its occurrence. If the subject received lirentelimab SC, the pregnancy should be followed to determine outcome, including spontaneous or voluntary termination, details of the birth, and the presence of absence of any birth defects, congenital abnormalities, or maternal and/or newborn complications. If the subject received lirentelimab SC, any SAE experienced during pregnancy must be reported on the SAE Report Form.

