14.2 Serious Adverse Events

A SAE is defined as an AE that meets that one of the following criteria:

- Death
- A life-threatening AE that places the subject at risk of death at the time of the event. It does not refer to an event that hypothetically might cause death if it were more severe.
- Inpatient hospitalization or prolongation of existing hospitalization.
- A persistent or significant disability/incapacity.
- A congenital anomaly/birth defect occurring in the offspring of a study subject.

• Other important medical events may also be considered a SAE when, based on appropriate medical judgment, they jeopardize the subject or require intervention to prevent any of the outcomes listed above.

Serious adverse events will be assessed and recorded beginning after the first administration of study drug and ending at Day 155 (\pm 5) or 84 (\pm 5) days after last dose, unless the SAE is related to a screening procedure, in which case it will be captured from the date of informed consent.

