14.8.3 Pregnancy Reporting

Pregnancies are captured if they occur in female subjects or in the sexual partners of male subjects from the time the subject is first exposed to the investigational product through the time of study completion or ET of the double-blind period or the OLE period, whichever is longer.

Female subjects must be instructed to discontinue all study drugs and inform the Investigator immediately if they become pregnant during the study. Male subjects must inform the Investigator immediately if their partner becomes pregnant during the study.

The Investigator must report any pregnancy to Allakos within 24 hours of becoming aware of it using the provided pregnancy reporting forms. Female subjects must be immediately discontinued from study drug. An uncomplicated pregnancy will not be considered an AE or SAE, but all pregnancies in subjects who received lirentelimab will be followed through term. For male subjects with female partners who become pregnant, the site will ask the father (the study subject) to provide information about the outcome of the pregnancy and information about the baby. If detailed health information about the mother is requested by Allakos, a Pregnant Partner Information Release Form will be provided to the site for the mother to sign.

Any congenital abnormalities noted at birth in the offspring of a subject who received lirentelimab will be reported as a SAE. If the subject received lirentelimab, the outcome of any pregnancy and the presence or absence of any congenital abnormality will be recorded in the source documentation and reported to the Medical Monitor and Sponsor via the pregnancy reporting form.

14.8.4 **AESI Reporting**

Beginning from the time of first SC injection of study drug and ending at the time of study completion or ET of the double-blind period or the OLE period, whichever is later, any new AESI (or new information related to a previously reported AESI) must be recorded in the AE eCRF and designated as an "AE of special interest."

For subjects participating in the OLE period, AESI will be assessed and recorded in the CRF of the AK002-027 double-blind treatment period database up until the start of the first OLE injection after the Day 85 visit and recorded in the CRF of the AK002-027 OLE period database beginning from the start of the first OLE injection after the Day 99 visit.

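### In the double-blind period, pregnancy follow-up, pregnancy SAE reporting and birth-defect reporting are worded to depend on receipt of lirentelimab, which a blinded site can establish only by unblinding

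*Protocol*

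**What the plan says.** Two sections set the duties after a pregnancy.

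- **Protocol 12.3.2** requires that "each pregnancy in a subject that received study drug must be reported within 24 hours of learning of its occurrence". It then narrows what follows: "If the subject received lirentelimab SC, the pregnancy should be followed to determine outcome", and "If the subject received lirentelimab SC, any SAE experienced during pregnancy must be reported on the SAE Report Form".
- **Protocol 14.8.3** begins without a condition: "The Investigator must report any pregnancy to Allakos within 24 hours of becoming aware of it". It then says that "all pregnancies in subjects who received lirentelimab will be followed through term", and that "Any congenital abnormalities noted at birth in the offspring of a subject who received lirentelimab will be reported as a SAE". A further sentence limits recording and reporting the pregnancy outcome in the same way. For a male subject whose partner becomes pregnant, the site asks him about the outcome and the baby, with no arm condition.

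The general SAE rules have no arm condition. The list of SAE criteria in 14.2 includes "A congenital anomaly/birth defect occurring in the offspring of a study subject", and 14.8.2 requires any SAE during the study to be reported, whether or not it is attributable to study drug. Section 14.2 ends SAE recording at Day 155 (±5) or 84 (±5) days after the last dose.

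On the blind, 11.3 names investigators, sponsor, research staff, subjects and the study monitor as blinded, and allows exceptions for emergency management and regulatory reporting. Section 11.4 repeats those grounds and adds a third: "if there is a pregnancy during the pregnancy reporting period". It lets the investigator or other registered site users unblind through the IRT. Section 10.1 defines study drug as covering both lirentelimab SC and placebo SC.

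**The concern.** A duty that depends on the arm cannot be carried out by someone who does not know the arm. A site with a double-blind pregnancy has three choices: unblind in order to learn what it must do, treat every subject as exposed, or treat the condition as unmet. The protocol does not say which. The first spends an unblinding on a reporting question. The third could leave a pregnancy SAE or a birth outcome unrecorded, including one in an exposed subject.

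The wording also leaves the SAE rules inconsistent on a safety outcome. A birth defect in a placebo subject's child is an SAE by the definition in 14.2, yet 14.8.3 calls for SAE reporting only where the subject received lirentelimab.

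**Working it through.** No figure in the plan bears on this point, so the check is a comparison of passages and one timing calculation.

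**1. Which duties depend on the arm**

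| Duty | Section | Depends on lirentelimab? |
|---|---|---|
| First report of a pregnancy, within 24 hours | 12.3.2, 14.8.3 | No |
| Reporting an SAE seen during the study | 14.8.2 | No |
| Birth defect counted as an SAE | 14.2 | No |
| Asking a male subject for the partner's outcome | 14.8.3 | No |
| Following a female subject's pregnancy to outcome | 12.3.2, 14.8.3 | Yes |
| Pregnancy SAE on the SAE Report Form | 12.3.2 | Yes |
| Abnormality at birth reported as an SAE | 14.8.3 | Yes |
| Recording the outcome and reporting it to the Medical Monitor and sponsor | 14.8.3 | Yes |

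**2. Do the unconditional rules cover the conditional ones?** For an SAE inside the collection window, yes: 14.8.2 applies in either arm. For a birth at term, the window has to be compared with the date of birth.

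- End of window (14.2): 155 + 5 = Day 160 at the latest. Counting from the last dose (Day 71 ±5), 71 + 5 + 84 + 5 = Day 165 at the latest.
- Assumption, not in the documents: term birth is 245 to 280 days after conception, and conception is no more than 14 days before Day 1.
- Earliest term birth: 245 − 14 = 231, so about Day 231. For conception on Day 1 the latest is 1 + 280 = Day 281. Later conceptions give later births.
- Shortest gap: 231 − 165 = 66 days after the window has closed.

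On these assumptions every term birth falls outside the general window, and the arm-conditional sentences are the only ones left to govern it. The same holds for SAEs late in a pregnancy. A loss or very early delivery inside the window falls under 14.8.2.

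**3. Can the site obtain the allocation?** Yes, through the IRT under 11.4. That section permits unblinding for pregnancy but does not require it, and neither 12.3.2 nor 14.8.3 refers to it. Nothing says who obtains the allocation, or when, before follow-up is decided.

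**4. 11.3 against 11.4.** Pregnancy is absent from the exceptions in 11.3 and present in 11.4.

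**5. Open-label extension.** Every subject there receives lirentelimab, so the condition is always met and no blinding question arises.

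**The case against.** The strongest reply is that the plan foresaw this. Section 11.4 names pregnancy as a ground for unblinding and gives the site the means, so a reader who infers that sites have no way to know the arm goes too far. That stands. It does not remove the problem, because unblinding is then the only way to apply the conditional sentences, and 11.3 does not list it.

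The second reply is that a sentence requiring reports for exposed subjects does not exempt the others, so 12.3.2 can be read alongside 14.8.2. Inside the SAE window this stands, and a reader should not infer that in-study SAEs in placebo subjects would be missed. After the window there is no unconditional rule to fall back on.

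Other strong inferences also lack support:

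- **That no placebo-arm pregnancy is followed, so a comparator is lost.** Male subjects in either arm are asked for the partner's outcome. The documents give no expected number of pregnancies, and nothing in them shows that a comparison between arms would be informative.
- **That unblinding for pregnancy has no medical purpose and the ground should be deleted.** The documents do not say whether knowledge of exposure matters to managing a pregnancy. They show only that 11.3 and 11.4 differ.
- **That the primary analysis is affected.** The wording in 11.4 could cover a male subject still dosing and keeping a diary, and unblinding is not an intercurrent event in SAP 4.2.4. But no number of such cases can be derived, and a pregnancy found after Day 85 comes after the Week 12 endpoint.

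Finally, following only exposed pregnancies in female subjects can be defended as a choice. It is still a choice that cannot be carried out blind.

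**Conclusion.** The point holds in limited form. In the double-blind period, follow-up to outcome in female subjects, pregnancy SAE reporting and the reporting of congenital abnormalities as SAEs are worded by receipt of lirentelimab. A blinded site can apply that wording only by obtaining the allocation, and it conflicts with the unconditional terms of 14.2 and 14.8.2. Sections 11.3 and 11.4 also disagree on pregnancy.

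The practical exposure is pregnancy SAEs and birth outcomes after about Day 155, and unblinding that reporting need not require. It rests on the assumed interval from conception to term birth; the shortest gap of 66 days leaves room for error in that assumption. Events are likely to be few, given the contraception requirements and about 130 subjects, but the documents support no rate. This is a wording defect on a safety outcome. No effect on the efficacy analysis is shown.

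**What to change.** - In 12.3.2 (two sentences) and 14.8.3 (three sentences), replace receipt of lirentelimab with *received study drug*, the term 10.1 already defines for both arms and 12.3.2 already uses for the first report. Pregnancy follow-up, pregnancy SAEs and birth outcomes are then collected in both arms without the allocation. These sentences carry no Day 155 limit, so they would also cover births after the general SAE window.
- Reconcile 11.3 with 11.4 on whether pregnancy is a ground for breaking the blind. Which way is for the sponsor to decide.
- State in 11.4 and 14.8.3 that unblinding is not needed to meet the pregnancy-reporting duties.

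The cost is an amendment of a few sentences, plus outcome follow-up of any placebo-arm pregnancies, for which the documents give no expected number.
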